6.6.6.4 Dose Modifications for Hepatotoxicity

AZD0466 dosing should be modified if a patient with normal or abnormal baseline liver function experiences a clinically significant and/or unacceptable change in hepatic biochemistry (including a DLT) described in [Table 10](#) and [Table 11](#) that is considered by the Investigator to be related to study intervention and not attributable to the disease (or to disease-related processes) under investigation.

Table 10 Dose Modification for Hepatotoxicity in Patients with Normal Baseline Liver Function

Event	Occurrence	Action with AZD0466
ALT and/or AST > 5 × ULN and ≤ 8 × ULN without concomitant elevation in bilirubin	First occurrence	
Withhold AZD0466 until values return to CTCAE Grade ≤ 1 or baselineRestart AZD0466 at same dose level if all values resolve to baseline or Grade ≤ 1 within 14 daysDiscontinue AZD0466 if the above criteria are not met
	Second occurrence	
Withhold AZD0466 until values return to CTCAE Grade ≤ 1 or baselineRestart AZD0466 at one lower dose (Table 7) if all values resolve to baseline or Grade ≤ 1 within 14 daysDiscontinue AZD0466 if the above criteria are not met
	Third occurrence	
Withhold AZD0466 until values return to CTCAE Grade ≤ 1 or baselineRestart AZD0466 following the Q2W schedule (Table 6) if all values resolve to baseline or Grade ≤ 1 within 14 days and after discussion with Study PhysicianDiscontinue AZD0466 if the above criteria are not met
	Fourth occurrence	
Withhold AZD0466 until values return to CTCAE Grade ≤ 1 or baselineRestart AZD0466 at one lower dose than the previous dose, maintaining the Q2W schedule (Table 6 and Table 7) if all values resolve to baseline or Grade ≤ 1 within 14 days, there is clear evidence of clinical benefit and after discussion with Study PhysicianDiscontinue AZD0466 if the above criteria are not met
ALT and/or AST > 8 × ULN and ≤ 20 × ULN without concomitant elevation in bilirubin	First occurrence	
Withhold AZD0466 until values return to CTCAE Grade ≤ 1 or baselineRestart AZD0466 at one lower dose (Table 7) if all values resolve to baseline or Grade ≤ 1 within 14 daysDiscontinue AZD0466 if the above criteria are not met

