8.3.1 Time Period and Frequency for Collecting AE and SAE Information

Adverse events and SAEs will be collected from the time of signature of the ICF throughout the treatment period and including the follow-up period (28 days after the last dose of the study intervention). If an event that starts after the defined safety follow-up period noted above is considered to be due to late-onset toxicity to study intervention, it should be reported as an AE or SAE as applicable.

All SAEs will be recorded and reported to AstraZeneca or its designee within 24 hours. The Investigator will submit any updated SAE data to AstraZeneca within 24 hours of it being available.

The method of recording, evaluating, and assessing causality of AEs and SAEs and the procedures for completing and transmitting SAE reports are provided in [Appendix B](#).

If the Investigator becomes aware of an SAE with a suspected causal relationship to study intervention that occurs after the end of the clinical study in a patient treated by him/her, the Investigator shall, without undue delay, report the SAE to the Sponsor.

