8.3.2 Follow-up of AEs and SAEs

After the initial AE/SAE report, the Investigator is required to proactively follow each patient at subsequent visits/contacts. All SAEs and non-SAEs will be followed until resolution, stabilisation, the event is otherwise explained, or the patient is lost to follow-up.

Any AEs that are unresolved at the patient's last AE assessment or other assessment/visit as appropriate in the study are followed up by the Investigator for as long as medically indicated (this may be beyond the 28 days after the last dose of study intervention), but without further recording in the eCRF. AstraZeneca retains the right to request additional information for any patient with ongoing AE(s)/SAE(s) at the end of the study, if judged necessary.

Adverse Event Variables

The following variables will be collected for each AE:

- AE (verbatim)
- The date when the AE started and stopped
- CTCAE grade/changes in CTCAE grade
- Whether the AE is serious or not
- Investigator causality rating against the investigational product(s) (yes or no)
- Action taken with regard to investigational product
- Outcome

In addition, the following variables will be collected for SAEs:

- Date AE met criteria for SAE
- Date Investigator became aware of SAE
- AE is serious due to
- Date of hospitalisation
- Date of discharge
- Causality assessment in relation to study procedure(s)
- Causality assessment to other medication
- Description of the SAE
- Probable cause of death

- Date of death
- Autopsy performed

The grading scales found in the revised NCI CTCAE v5.0 will be utilised for all events with an assigned CTCAE grading. For those events without assigned CTCAE grades, the recommendation in the CTCAE criteria that converts mild, moderate, and severe events into CTCAE grades should be used. A copy of the CTCAE v5.0 can be downloaded from the CTEP website (<http://ctep.cancer.gov>).

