10.4.1 Overall Design

Module 1 will evaluate the safety, tolerability, PK, and efficacy of AZD0466 as monotherapy. Module 1 comprises 2 parts: AZD0466 monotherapy dose escalation in patients with advanced B-NHL (Part A) followed by 3 independent dose expansion cohorts of patients with defined lymphoid malignancies (Part B). The Module 1 schema is illustrated in [Figure 2](#).

- **Part A:** Phase 1 dose setting to assess the safety and tolerability and determine dose(s) and schedule(s) to be evaluated in Part B.
- **Part B:** Phase 1b/2a dose expansion to assess the efficacy of AZD0466 in 3 select patient populations: R/R MCL (Cohort B1), R/R FL or MZL (Cohort B2), and R/R DLBCL (Cohort B3).

An SRC will be responsible for making recommendations for dose escalation or dose de-escalation decisions after each dose level. The SRC will also assess all evaluable patients to establish the RP2D and determine if the study should progress to Part B. Refer to [Appendix A 5](#) for details of the SRC.

Treatment will be administered in the outpatient setting with close monitoring. All patients will be treated until progressive disease or unacceptable toxicity or withdrawal of consent. All patients should be followed for survival every 3 months until death. Patients who discontinue treatment due to unacceptable AEs should be followed until resolution or stabilisation of the AE, then for response and survival. Patients who achieve a CR will be followed for relapse of disease until death.

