4.3.8 Missing Dates

Generally, the imputation of dates is used to decide if an observation is treatment emergent for adverse events or concomitant medications. The imputed dates should not be used to calculate durations, where the results would be less accurate.

The following are the guidelines used when partial dates are detected in the study:

- For missing diagnostic dates (e.g., disease diagnosis), if the day and/or month are missing use 01 and/or Jan. If year is missing, put the complete date to missing
- For missing AE or concomitant medication start dates the following will be applied:
 - a. Missing day: Impute the 1st day of the month unless month is the same as month of first dose of study treatment then impute first dose date.
 - b. Missing day and month: Impute 1st January unless year is the same as first dose date then impute first dose date.
 - c. Completely missing: Impute first dose date unless the end date suggests it could have started prior to this in which case impute the 1st January of the same year as the end date.
 - d. Imputed start date should be no later than the end date.
- For missing AE or medication end dates, the following will be applied:
 - a. Missing day - impute the last day of the month unless both the month and the year are the same as the last dose date or the primary analysis data cut-off date then impute the last dose date or the primary analysis data cut-off date.
 - b. Missing day and month - impute 31st December unless the year is the same as the last dose date or the primary analysis data cut-off date then impute the last dose date or the primary analysis data cut-off date.
 - c. Completely Missing – need to look at whether the AE/medication is still ongoing before imputing a date and also when it started in relation to study drug. If the ongoing flag is missing then assume that AE is still present / medication is still being taken (i.e. do not impute a date). If the AE/medication has stopped and start date is prior to first dose date then impute first dose date. Or if it started on or after first dose date then impute a date that is after the last dose of study drug date.
- Flags will be retained in the datasets indicating where any programmatic imputation has been applied, and in such cases, any durations would not be calculated.

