- Non-serious AEs occurring in greater than 5% of patients
- SAEs by SOC and PT

SAEs

SAEs will be summarised as described above for the TEAEs.

AEs of special interest

Grouped summary tables of certain MedDRA preferred terms will be produced and may also show the individual preferred terms which constitute each AESI grouping. Groupings will be based on preferred terms provided by the medical team prior to DBL, and a listing of the preferred terms in each grouping will be provided.

Summaries of the above-mentioned grouped AE categories include number and percentage (%) of patients who have:

- At least one AESI presented by event outcome
- At least one AESI causally related to IP
- At least one AESI leading to discontinuation of study treatment.

A summary of total duration (days) of AESI will be provided for events which have an end date, and this may be supported by summaries of ongoing AESIs at death and, separately, at data cut-off.

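### The only planned AESI duration summary (SAP 5.6.2.2) uses resolved events alone; read as time to resolution, it is too short in expectation when some AESIs are still open at data cut-off or when AE recording ends

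*SAP*

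**What the plan says.** SAP 5.6.2.2, under AEs of special interest, commits to one statistic on how long these events last: "A summary of total duration (days) of AESI will be provided for events which have an end date". The complement is left optional: "this may be supported by summaries of ongoing AESIs at death and, separately, at data cut-off". Neither document plans another AESI duration statistic. The same section does commit to counting patients with "At least one AESI presented by event outcome".

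Three rules decide which events have a usable end date:

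- SAP 4.3.8: if the end date is completely missing and there is no ongoing flag, the analyst is to "assume that AE is still present / medication is still being taken (i.e. do not impute a date". Durations are not computed from imputed dates in any case.
- Protocol 8.3.1: AEs are collected from consent through treatment, "including the follow-up period (28 days after the last dose of the study intervention".
- Protocol 8.3.2: AEs are followed to resolution or stabilisation, but those unresolved at the last assessment are then followed for as long as medically indicated, "but without further recording in the eCRF".

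Two provisions work the other way. Protocol 10.4.1 says: "Patients who discontinue treatment due to unacceptable AEs should be followed until resolution or stabilisation of the AE"; section 10.6.6.2 repeats this. Protocol Appendix E 4.2 requires potential Hy's Law cases to be monitored until liver values return to normal or baseline (or as long as medically indicated), with the liver eCRF modules completed as information arrives.

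The AESIs are tumour lysis syndrome, hepatotoxicity and a QRS amplitude change.

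**The concern.** An AESI enters the duration table only if it ends before recording stops, so the longer it lasts, the less likely it is to be counted. A reader may then take the duration among those seen to recover as the duration of the toxicity itself.

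Slow hepatotoxicity is the likeliest case. Under Protocol Tables 10 and 11, a transaminase rise that has not settled within 14 days generally ends treatment. The 28-day collection period runs from the last dose, which comes before the hold. The slowest liver events are therefore the ones most likely to be open when routine collection ends.

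The SAP handles the same structure differently for duration of response. Sections 5.2.3.2 and 5.2.3.3 keep open intervals, censor them and use Kaplan-Meier.

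**Working it through.** **1. The plan's own figure.** There is none to reproduce. Neither document gives an expected AESI duration or an expected share of open events.

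**2. Direction.** Let T be the time from onset to resolution, with density f and distribution function F. Let C be the time from onset to the end of recording. The event is counted if T ≤ C. If C is independent of T, the density among counted events is proportional to f(t) × P(C ≥ t). The second factor cannot rise with t, so E[T | T ≤ C] ≤ E[T], and the inequality is strict once long events are lost. If both times are exponential and a share q is open, the counted mean is E[T] × (1 − q). A true mean of 28 days becomes 25.2, 22.4, 19.6 or 14.0 days for q of 10, 20, 30 or 50%.

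This is a statement about expectation. In simulated sets of 20 events (exponential, mean 28 days, C uniform on 0 to 56 days, about 43% open), the counted mean fell below 28 days in 99.98% of sets, not all of them.

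**3. Size, spread onset.** From Protocol 8.3.1: 28 days of recording after the last dose. Assumed: 28 days is a hard stop; onset is uniform over 112 treatment days; durations are exponential or lognormal with log-SD 0.8. Then P(C ≥ t) = 1 up to day 28 and (140 − t)/112 from day 28 to day 140. The median m among ended events solves ∫₀ᵐ f(t)P(C ≥ t)dt = 0.5 × P(ended).

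Worked case, exponential with true median 28: P(ended) = 1 − 2⁻¹ × (1 − 2⁻⁴)/(4 ln 2) = 1 − 0.5 × 0.9375/2.7726 = 0.831. Half is 0.4155, which is below F(28) = 0.5, so m = 28 × log₂(1/0.5845) = 21.7 days. The shortfall is (28 − 21.7)/28 = 22.5%. The other rows come from numerical integration of the same equation.

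| True median (days) | Ended, exp. | Median, exp. | Ended, lognormal | Median, lognormal | Shortfall |
|---|---|---|---|---|---|
| 7 | 0.994 | 6.9 | 0.995 | 7.0 | under 1% |
| 14 | 0.955 | 13.1 | 0.967 | 13.6 | 3 to 6% |
| 28 | 0.831 | 21.7 | 0.865 | 24.4 | 13 to 23% |
| 56 | 0.617 | 29.8 | 0.640 | 39.1 | 30 to 47% |

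**4. Size, extreme case.** If every AESI started at the last dose, C = 28 and m solves F(m) = 0.5 × F(28). For the exponential with true median 28: F(28) = 0.5, so m = 28 × log₂(1/0.75) = 11.6 days. For true medians of 7, 14, 28 and 56 days, the counted medians are 6.4, 9.5, 11.6 and 12.8 days (exponential) or 6.7, 11.5, 16.3 and 19.8 days (lognormal).

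**5. Events open at death.** Take exponential times with means of 28 days (resolution) and 60 days (death). The mean among events that resolve first is 1/(1/28 + 1/60) = 1680/88 = 19.1 days. The mean time with the event while alive, E[min(T, death)], is also 19.1 days. There is no shortfall for that target, but there is one against 28 days if time to resolution is meant.

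**6. Check of the remedy.** Repeat episodes occur within a patient; Protocol Table 10 provides for a "Fourth occurrence". The check simulated 15 patients with 1 to 4 episodes each (between-patient log-SD 0.7, within-patient 0.4, the window of step 3, 4,000 replicates; all assumed). The 95% CI for the Kaplan-Meier median covered the truth in 82 to 83% of replicates when episodes were treated as independent, and in 94 to 95% with the first episode per patient. Typical first-episode medians were 7.0, 14.0, 28.0 and 56.3 days, against 7.0, 13.6, 24.3 and 39.0 from ended events only. The median was not reached in at most 2.5% of replicates.

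**The case against.** The best defence is that the SAP states the restriction openly and does not call the figure a time to resolution. Much of the missing information also appears elsewhere. The by-outcome counts are mandatory, and outcome is collected for every AE (Protocol 8.3.2), so patients with unresolved AESIs will be visible. AEs are listed individually (Protocol 9.4.3.1, SAP 5.6.2.2). Recovery can also be seen in the by-visit laboratory and ECG summaries and the TLS outputs (SAP 5.6.4.2, 5.6.9.2, 5.6.8.2). Follow-up after stopping for an AE, and the liver modules for potential Hy's Law cases, may supply some late end dates. Table specifications sit in a separate document (SAP 1), so the optional counts may well be produced.

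All of this stands and limits the point. It does not remove it: none of these outputs is a duration that includes open events, and the follow-up provisions do not expressly promise an AE stop date.

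A reader might infer that unresolved AESIs vanish from the report. The by-outcome table shows otherwise. A reader might also infer that nothing can be recorded after day 28. Protocol 8.3.2 ties the end of eCRF entry to the last AE assessment or other appropriate visit, and Appendix E continues liver recording, so the extreme case in the working is a bound under assumption, not a forecast.

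**Conclusion.** The point holds as a minor one. Read as time to resolution, the planned statistic is too short in expectation when some AESIs are open at DCO or at the end of AE recording, provided recording stops independently of duration.

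The documents do not support the stronger reading that the figure is biased downward whenever any AESI is unresolved. The direction need not hold in every sample, and for events open at death it depends on the target.

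The size cannot be found from the documents. It is likely negligible for AESIs that resolve in about a week and could matter for those lasting several weeks. The 112-day spread, the duration distributions and the 28-day hard stop are all assumptions; planned treatment runs up to 2 years. No primary endpoint, MTD rule or recruitment-pause rule uses AESI duration.

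**What to change.** In SAP 5.6.2.2:

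1. Keep the total-duration table, which covers repeat episodes, and label it *resolved events only*.
2. Make the ongoing summaries mandatory: the table *will be accompanied by the number of* AESIs ongoing at death and, separately, at DCO.
3. Add a supplementary descriptive time to resolution for the first episode per patient per AESI grouping. Censor open events at the earlier of last AE assessment or DCO, and give the Kaplan-Meier median where numbers allow. Report deaths with the AESI unresolved separately.
4. When events are few, replace item 3 with a listing of durations carrying a censoring flag.

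The cost is a small wording change and one added descriptive output from data already collected, with no protocol amendment. The downside is that the median may be imprecise or not reached, and first-episode results say nothing about later episodes, which is why item 3 supplements the existing table and does not replace it.

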5.6.3 Death

5.6.3.1 Presentations

A summary of deaths will be provided with the number and percentage of patients categorised as:

- Related to disease under investigation only
- AE outcome = death only
- Both related to disease under investigation and with AE outcome = death
- AE with outcome = death > 30 days after last study treatment
- Other deaths

A corresponding listing will also be produced.

5.6.4 Clinical Laboratory, Blood Sample

5.6.4.1 Definitions and Derivations

Laboratory tests will be grouped according to chemistry and haematology

For chemistry and haematology parameters, laboratory abnormalities with toxicity grades according to the National Cancer Institute (NCI) CTCAE version 5.0 will be derived. Laboratory variables that will be measured are detailed in [Table 3](#).

Table 3 Laboratory Safety Variables

| Haematology/Haemostasis (whole blood) | | Clinical Chemistry (serum or plasma) | |
|--|--|---|-----------------------------------|
| Haemoglobin (Hb) | | Creatinine | Chloride |
| Leukocyte count (WBC count) | | Bilirubin, total | Cortisol ^a |
| Leukocyte differential count | | Alkaline phosphatase | TSH ^a |
| Neutrophils | | AST | Bicarbonate |
| Lymphocytes | | ALT | BUN/urea nitrogen |
| Eosinophils | | Amylase ^b | Lipase ^b |
| Platelet count | | Albumin | LDH |
| Urinalysis | | Potassium | Phosphate |
| Hb/erythrocytes/blood | | Calcium, total | Uric acid |
| pH | Ketones | Sodium | Troponin I ^a |
| Protein/albumin | Bilirubin | BNP (or NTproBNP) ^a | |
| Glucose | | Magnesium | Glucose |
| Microscopy (red and white blood cells, bacteria, casts, and crystals) only if urinalysis is abnormal | | Total protein | ACTH ^a |
| Coagulation | | Cholesterol | GGT |
| International normalised ratio (INR) | | Triglycerides | Ferritin |
| Activated partial thromboplastin time (aPPT) | | High-density lipoprotein (HDL) | Creatine kinase (CK) |
| Prothrombin time (PT) | | Low-density lipoprotein (LDL) | |
| Fibrinogen | Pregnancy test (females of childbearing potential only) | | |
| Viral Serology | | Urine human chorionic gonadotropin (hCG) | Serum beta hCG |
| Hepatitis B and C | CMV | Others | |
| SARS-CoV-2 | | Serum immunoglobulins ^a | Beta-2 microglobulin ^a |

^a At screening, at target dose (pre dose timepoint) and then as clinically indicated and at end of treatment visit.

^b Collected at screening, pre-infusion on each dosing day, and end of treatment visit.

Lipids: triglycerides, high density lipoprotein, low density lipoprotein, and cholesterol.

ACTH = adrenocorticotrophic hormone; ALT = alanine aminotransferase; AST = aspartate aminotransferase; BUN = blood urea nitrogen; CMV = cytomegalovirus; GGT = gamma-glutamyltransferase; LDH = lactate dehydrogenase;

SARS-CoV-2 = severe acute respiratory syndrome coronavirus 2; TSH = thyroid-stimulating hormone; WBC = white blood cell.

Change from baseline in haematology and clinical chemistry endpoints will be calculated for each post-dose visit. CTC grade is calculated at each visit for tests with CTC grading

defined. Maximum post-baseline CTC will be also calculated. Absolute values will be compared to the local laboratory reference range and classified as low (below range), normal (within range or on limits of range) and high (above range). All values classified as high or low will be flagged on the listings.

Liver Function Parameters

Patients with elevated post-baseline alanine aminotransferase (ALT), aspartate aminotransferase (AST) or Total Bilirubin that fall into these categories will be identified. The number and percentages of these patients will be tabulated for the following parameters in **Table 4**.

Table 4 Liver Function Parameters

| Liver Function Parameters | Category |
|---------------------------|---|
| ALT | 
 • $\geq 3 \times - \leq 5 \times$ ULN • $> 5 \times - \leq 8 \times$ ULN • $> 8 \times - \leq 10 \times$ ULN • $> 10 \times - \leq 20 \times$ ULN • $> 20 \times$ ULN |
| AST | 
 • $\geq 3 \times - \leq 5 \times$ ULN • $> 5 \times - \leq 8 \times$ ULN • $> 8 \times - \leq 10 \times$ ULN, • $> 10 \times - \leq 20 \times$ ULN • $> 20 \times$ ULN |
| Total bilirubin | 
 • $\geq 2 \times - \leq 3 \times$ ULN • $> 3 \times - \leq 5 \times$ ULN • $> 5 \times$ ULN |
| ALT or AST | 
 • $\geq 3 \times - \leq 5 \times$ ULN • $> 5 \times - \leq 8 \times$ ULN • $> 8 \times - \leq 10 \times$ ULN, • $> 10 \times - \leq 20 \times$ ULN • $> 20 \times$ ULN |
| Potential Hy's law | 
 • (AST $\geq 3 \times$ ULN or ALT $\geq 3 \times$ ULN) and (Total Bilirubin $\geq 2 \times$ ULN)a |

ULN: upper limit of normal range.

It includes all patients who have ALT or AST $\geq 3 \times$ ULN and total bilirubin (BILI) $\geq 2 \times$ ULN, and in which the elevation in transaminases precede or coincide with (that is, on the same day as) the elevation in BILI.

